### **Investigational device related risks**

#### *THERMOCOOL SMARTTOUCH® SF-5D catheter and nMARQ Multi-Channel RF generator with TGA mode*

Although the risks are low, anticipated risks /major complications associated with the catheter ablation procedure in general could still occur during the procedure. During the TGA design phase (ref RBA section 6.1.1), systematic proactive risk analyses concluded that no new hazards and harms associated with TGA (FAST mode) have been identified to cause any foreseeable risks. At this juncture, no new complications are anticipated concerning the TGA ablations.

The nMARQ™ Multi-Channel RF Generator (D-1341-07) (SW version 2.3.1) was CE marked on Oct 25, 2013. In order to allow for an interface with the THERMOCOOL SMARTTOUCH® SF-5D Catheter, the software was modified to SW version 3.0.1. As a result of the software modification, the nMARQ™ Multi-Channel RF Generator will be designated as an investigational device. Further reference can be made to the User manual and addendum, for more information. Enhanced versions of the SW v3.0.1 might be released and used during the course of this study. A protocol Amendment will be submitted for approval if any additional significant risks would be identified in newly released software versions.

The software with TGA mode using the investigational catheter has been validated in both bench top and animal testing at the system level. The design of the software has been independently validated to perform against functional requirements. Accuracy of the generator as it relates to: temperature and power was identified to be the highest risk related to the device. Therefore, 100% testing of generator power, temperature and impedance is included in the lot release protocol, prior to the release to the study.

Robust testing of the devices from the component and the system level, within simulated clinical conditions, including certain up limits & extreme clinical scenarios, was determined to be successful with no adverse events identified.

For SW V3.0.1 there are no anticipated potential direct risks to the subject, the risk is mitigated by the temp cutoff setting of the generator and the optimization of the target temperature. Further reference can be made to the pre-clinical testing reports and Investigator Brochure for more information.

#### 1.4.2. ***Minimization of Risk***

The criteria for subject selection, methods, personnel, facilities, and training that have been specified in this study are intended to minimize the risk to subjects undergoing this procedure.

**Patient selection:** Subjects will be screened carefully prior to enrollment in the study to ensure compliance with the inclusion and exclusion criteria. The exclusion criteria have been developed to exclude subjects with a medical history or condition that increases their risk of adverse events (refer to Section 4.2 for the Exclusion Criteria).

**Pre-procedure imaging:** All subjects will have pre-procedure imaging as described in section 8.2 to screen for the presence of LA thrombus, which is intended to decrease the potential for thromboembolic complications.

**Within procedure safeguard:** Investigators will undergo training on the use of the THERMOCOOL SMARTTOUCH® SF-5D technology prior to subject enrollment. Investigators skilled in intracardiac mapping and ablation of AF with the use of RF ablation catheters containing contact force technology will be selected for participation in the study. All investigators are required to receive the training prior the enrollment. AF ablation procedures will be performed in electrophysiology laboratories with the assistance of skilled nurses and technicians. The detailed workflow for the procedure is provided in the protocol, including the target temperature, the cut-off temperature, the range of the contact force, the stability using Visitag, Respiratory compensation and Automatic tags. To proactively manage the four big “watch-out” complications (Atrio-Esophageal Fistula, PV stenosis, Phrenic nerve paralysis and cerebral embolism) for a RF ablation procedure, the protocol proposes the following:

- In order to prevent esophageal injury, intraluminal esophageal monitoring is required for the study
- The risk of cerebral lesions will be monitored by pre-post cerebral MRI examination monitoring for cerebral embolism.
- The risk of PV stenosis will be minimized by monitoring that RF energy applications are at least 1 to 2 cm outside the PV ostium to isolate the left and right-sided PVs; Subjects presenting suggestive symptoms for PV stenosis, should undergo the cardiac CT/MRI;
- The risk of PNP will be minimized by monitoring the PN with pacing maneuvers before the ablation. High output pacing is recommended at vulnerable sites and avoid ablations at the area that stimulate the PN

**Post-procedural management:** In accordance with the 2017 HRS expert consensus statement, all subjects will be recommended to be maintained on systemic oral anticoagulation therapy for at least two months post-procedure, beginning within 6 hours post-procedure. After two-months post-procedure, a decision regarding continuation of systemic anti-coagulation agents will be based on the patient risk for thromboembolism. Systemic oral anticoagulation will be recommended to be continued beyond two-months post-ablation in patients with CHA2DS2-VASc score ≥2.

Safety data during enrollment and follow-up will be closely monitored and evaluated per the specific safety management plan for the study. Also, refer to safety section 9 for more information on safety management.

#### 1.4.3. **Known Potential Benefits**

The Biosense Webster THERMOCOOL SMARTTOUCH® SF-5D Catheter is a steerable multi-electrode luminal catheter with a deflectable tip designed to facilitate electrophysiological mapping of the heart and to transmit radiofrequency (RF) current to the catheter tip electrode for ablation purposes. In addition to force-sensing technology, the catheter incorporates six thermocouple temperature sensors and three micro electrodes embedded in the 3.5 mm tip electrode.

The measured temperature can be used by the operator to assess the efficiency of ablation in real time. The localized temperature measurement will provide a highly sensitive measure of catheter location stability and/or movement during RF application and may reduce the need for additional RF applications.

The micro electrodes will provide high quality localized electrograms that will allow finer endocardial electrical mapping and a better assessment of possible conduction gaps in the ablation lesion sets used to isolate the pulmonary veins and determining bidirectional block of linear lesion sets.

Finally, the catheter tip has incorporated a new angled design of the irrigation ports. This new design allows for reduced incidence/risk of charring and coagulum on the catheter increasing safety during the ablation procedure.

With improved contact force information and temperature feedback in any tip tissue orientation, the new THERMOCOOL SMARTTOUCH® SF-5D catheter is designed to create durable lesions, in shorter time, with fewer ablation applications, and improved irrigation flow decreasing the opportunity for char and coagulum formation.

The expected benefits of the THERMOCOOL SMARTTOUCH® SF-5D Ablation System: nMARQ™ Multi-Channel RF Generator (D-1341-07, SW version 3.0.1) and THERMOCOOL SMARTTOUCH® SF-5D catheter may improve safety and efficiency. The System may potentially:

- Limit conductive heating and collateral damage to neighboring structures including non-cardiac adjacent tissues.
- Increase catheter stability and reduce tissue edema, therefore improve lesion to lesion consistency at high-power for a short duration, giving that catheter instability in a constantly mobile heart and tissue edema remains problematic for the effective lesions using the conventional ablation technique.
- Contact force sensing capabilities and improved temperature feedback may aid in increasing the effectiveness of RF ablations by maintaining better control for a more effective lesion formation.
- Reduce the procedural time related to ablating the pulmonary vein triggers in the left atrium and improve the PVI efficiency significantly.
- Reduce fluoroscopy exposure for both the patient and the staff.
- Microelectrodes may aid in better assessment of possible conduction gaps in the ablation lesion sets.
- Reduce the amount of fluid loading of the patient as compared to a focal ablation catheter.

Further reference can be made to the Risk-Benefit Analysis (RBA) for more information.

## 2. Objectives

The primary objective of this clinical investigation is to assess the safety and acute performance of the THERMOCOOL SMARTTOUCH® SF-5D system used with the TGA algorithm, in the isolation of the atrial pulmonary veins in treatment of patients diagnosed with Paroxysmal Atrial Fibrillation (PAF). Specifically, to demonstrate:

- Safety based on the incidence of early onset Primary Adverse Events (PAEs) (within seven (7) days of the initial ablation procedure).
- Acute system performance based on acute procedural success defined as confirmation of entrance block in all targeted PVs after adenosine and/or isoproterenol challenge.

Secondary objectives of the study relate to further evaluation of safety with regards to (serious) adverse events and neurological incidents up to 3 months following procedure. Secondary evaluation of effectiveness and workflow will be done through characterization of the TGA and Q-mode use for PVI, assessment of acute reconnection during the procedure and through description of procedural parameters.

## 3. Study Design and Endpoints

### 3.1. Description of the Study Design

The QDOT-FAST study is a prospective, multi-center, non-randomized clinical study to evaluate the safety and acute performance of the THERMOCOOL SMARTTOUCH® SF-5D system with the TGA algorithm in patients diagnosed with Paroxysmal Atrial Fibrillation (PAF).

The study population will consist of up to 50 subjects with PAF as an indication for radiofrequency (RF) ablation. PAF is defined as AF that terminates spontaneously or with intervention within 7 days of onset. Episodes may recur with variable frequency (HRS ACC guidelines, 2017).

The study will be conducted at up to 10 sites in Europe. Follow-up will be conducted at 7 days, 1 month and 3-month post-ablation procedure.

### 3.2. Study Endpoints

#### 3.2.1. Primary Endpoint(s)

##### Acute Safety

The primary safety endpoint is the incidence of Primary Adverse Events (PAEs) (within seven (7) days of the initial mapping and ablation procedure). Primary Adverse Events are one of the following adverse events listed below. (refer to section 9.1.3 for a complete list and description/criteria).

Atrio-Esophageal Fistula (AEF)*	Phrenic Nerve Paralysis (PNP)
Cardiac Tamponade/perforation	Pulmonary Vein Stenosis*
Death*	Stroke/CVA
Major Vascular Access Complication/Bleeding	Thromboembolism
Myocardial Infarction	TIA

\* Device or procedure related death, pulmonary vein stenosis and atrio-esophageal fistula, that occur greater than one week (7 days) post-procedure are considered and analyzed as primary AEs.

### Acute Effectiveness

Acute procedural success defined as confirmation of entrance block in all targeted PVs after adenosine and/or isoproterenol challenge.

#### 3.2.2. *Secondary Endpoint(s)*

##### Safety

- Incidence of Serious Adverse Device Effects (SADEs)
- Incidence of Serious Adverse Events (SAEs) within 7 days (early-onset), >7-30 days (peri-procedural) and >30 days (late onset) of initial ablation procedure
- Incidence of non-serious adverse events
- Incidence of pre-and post-ablation asymptomatic and symptomatic cerebral emboli as determined by MRI evaluations
- Incidence of new or worsening neurological deficits compared to baseline
- Summary of NIHSS, mRS and MoCA scores at baseline and follow-up timepoints

##### Effectiveness

- PVI achieved with TGA mode only among all targeted veins and by subject
- PVI achieved with combined use of TGA and Q-mode among all targeted veins and by subject
- Ablation of acute reconnection (touch-up) among all targeted veins and by subject
- Touch-up applications with TGA, Q-mode and non-study catheter applications
- PV ablation by a non-study catheter among all targeted veins and by subject

##### Additional analyses on procedural data, including but not limited to:

- Use of QDOT Micro™ catheter ablation outside the PV area
- Use of a non-study catheter for ablation outside the PV area
- Total procedure time, mapping time, PV ablation time, total ablation time, RF application time, LA dwell time
- Total number of RF applications, % TGA applications and % Q-mode applications
- Anatomical location of touch-up applications
- Temperature, power, contact force, impedance
- Total Fluoroscopy time/dose

## 4. Study Population

### 4.1. Participant Inclusion Criteria

Subjects must meet ALL the following inclusion criteria to be eligible for participation in this clinical investigation:

1. Age 18 or older.
2. Signed the Patient Informed Consent Form (ICF).
3. Diagnosed with symptomatic PAF
4. Selected for catheter ablation through pulmonary vein isolation.
5. Able and willing to comply with all pre-, post-, and follow-up testing and requirements (i.e. patient not confined by a court ruling).

## 4.2. Participant Exclusion Criteria

Subjects who meet ANY of the following exclusion criteria are not eligible for enrollment:

1. Atrial fibrillation secondary to electrolyte imbalance, thyroid disease, or reversible or non-cardiac cause.
2. Previous surgical or catheter ablation for atrial fibrillation.
3. Previously diagnosed with persistent, longstanding AF and/or continuous AF >7 days, or >48 hrs. terminated by cardioversion.
4. Documented Left Atrial thrombus on baseline/pre-procedure imaging.
5. Any carotid stenting or endarterectomy.
6. Left atrial (LA) size >50mm.
7. Left Ventricular ejection fraction (LVEF) <40%.
8. Uncontrolled heart failure or New York Heart Association (NYHA) function class III or IV.
9. History of blood clotting or bleeding abnormalities
10. Contraindication to anticoagulation
11. History of a documented thromboembolic event (including transient ischemic attack (TIA)) within the past 12 months.
12. Previous percutaneous coronary intervention (PCI) or myocardial Infarction (MI) within the past 2 months.
13. Coronary artery bypass grafting (CABG) in conjunction with valvular surgery, cardiac surgery (e.g. ventriculotomy, atriotomy) or valvular cardiac (surgical or percutaneous) procedure.
14. Rheumatic Heart Disease
15. Awaiting cardiac transplantation or other cardiac surgery within the next 12 months.
16. Unstable angina.
17. Significant pulmonary disease (e.g. restrictive pulmonary disease, constrictive or chronic obstructive pulmonary disease) or any other disease or malfunction of the lungs or respiratory system that produces chronic symptoms.
18. Acute illness, active systemic infection, or sepsis.
19. Presence of atrial myxoma, interatrial baffle or patch
20. Presence of intramural thrombus, tumor or other abnormality that precludes catheter introduction or manipulation.
21. Presence of a condition that precludes vascular access.
22. Presence of implanted pacemaker or implantable cardioverter-defibrillator (ICD).
23. Presence of IVC filter
24. Significant congenital anomaly or a medical problem that in the opinion of the investigator would preclude enrollment in this trial.
25. Currently enrolled in an investigational study evaluating another device, biologic, or drug.
26. Women who are pregnant (as evidenced by pregnancy test if pre-menopausal), lactating, or who are of child bearing age and plan on becoming pregnant during the course of the clinical investigation.
27. Life expectancy or other disease processes likely to limit survival to less than 12 months.
28. Presenting contra-indication for the devices used in the study, as indicated in the respective instructions for use.
29. Categorized as vulnerable population and requires special treatment with respect to safeguards of well-being
30. Contraindication to use of contrast agents for MRI such as advanced renal disease, etc. (at PI discretion)
31. Presence of iron-containing metal fragments in the body
32. Unresolved pre-existing neurological deficit.

## 4.3. Participant Withdrawal or Termination

### 4.3.1. Reasons for Withdrawal or Termination

Participants are free to withdraw from participation in the study at any time upon request without penalty or loss of benefits to which they may otherwise be entitled. Participants will be informed prior to study entry that they are free to withdraw from the study at any time and for any reason without prejudice to their future medical care by a physician or the institution.

An investigator may terminate a subject's participation in the study if:

- Any clinical adverse event (AE), laboratory abnormality, or other medical condition or situation occurs such that continued participation in the study would not be in the best interest of the participant
- Withdrawal is in the subjects' best interest
- The participant no longer meets eligibility criteria or meets an exclusion criterion (either newly developed or not previously recognized) that precludes further study participation.
- Subject withdraws consent
- Subject is lost to follow up

Every subject should be encouraged to remain in the study until they have completed the protocol required 3-months follow-up period.

### 4.3.2. Handling of Participant Withdrawals or Termination

If a subject is removed or withdraws from the study, the date and reason for withdrawal will be recorded on the appropriate electronic case report form (eCRF). If the subject is withdrawn due to an adverse event (AE) or serious adverse event (SAE), the Investigator should follow the subject until the AE/SAE has resolved or is considered stable.

If a subject is unable to return for an office/clinic visit or cannot be contacted by telephone, 3 separate telephone calls should be made to obtain subject related safety information. All attempts should be documented in the source documents. If the subject does not respond to the 3 telephone calls, then the investigator must send a certified letter to the subject. If the subject does not respond to the letter, then the subject will be considered "lost to follow-up" for the study.

Subjects who have signed the ICF, but are later found not to be eligible PRIOR to insertion of the study catheter will be excluded and will not count for the enrollment goal of 50 subjects. Excluded subjects can be replaced with new enrolled subjects for the study to reach a total of 50 evaluable study-subjects.

## 4.4. Subject Enrollment Disposition

The following subject groups are defined:

- **Enrolled Subjects:** Patients who sign the informed consent form.
- **Excluded Subjects:** Subjects who are enrolled but never undergo insertion of the study catheter. Excluded subjects will only be followed between ICF signature and exclusion for event reporting.

- **Evaluable Subjects:** All enrolled subjects who have the study catheter inserted.
- **Discontinued Subjects:** Enrolled subjects who have the study catheter inserted but do not undergo ablation (i.e., no RF energy is delivered with the study catheter). Discontinued subjects will remain in follow-up for 30 days.
- **Lost to Follow-up Subjects:** Evaluable subjects of which contact is lost after most recent visit (despite 3 documented attempts to contact the subject).
- **Withdrawn / Early Termination Subjects:** Subjects who withdraw consent for study participation or are withdrawn by the investigator, are terminated from the study prior to completion of all follow-up visits.
- **Completed Subjects:** Enrolled subjects who have not been excluded, discontinued, expired, withdrawn, terminated early, or lost-to-follow-up from the study prior to the final study visit.

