### **8.2.2.3 Study Ablation Procedure Sequence**

Subjects will arrive to the electrophysiology laboratory for their ablation procedure and will undergo preparation for the procedure per the hospital's standard protocol (discretion of investigator).

The AF ablation procedure for this study should follow this sequence:

- Transseptal puncture
- Mapping (left atrial anatomical map) is required prior to the ablation procedure.  
Note: An anatomical map is not required for triggers outside the left atrium (e.g. SVC/CS etc.)
- Ensure Esophageal monitoring
- Confirmation of target ACT 300-400 PRIOR to insertion of the study catheter into the left atrium and maintain throughout the procedure
- Introduction of the study catheter
- Complete PV encirclement with TGA mode as the primary mode for ablation (refer to NOTE 1 below). Q-mode can be used where the investigator deems TGA mode unable to achieve PVI.
- Confirmation of PV isolation in all targeted PV's
- Waiting period (20 minutes) and Isoproterenol/adenosine challenge
- Confirmation of entrance block in all targeted PV's

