### **14.6. Analysis Sets**

The following analysis populations will be used to complete the analyses of data:

- **Safety Population:** The safety population will include all enrolled subjects who have the investigational device inserted, regardless if RF energy is delivered.
- **Effectiveness Population:** The effectiveness population will include all enrolled subjects who have had the investigational device inserted and underwent ablation with the study catheter used in conjunction with TGA mode for PVI. The subjects without any TGA mode application for PVI will be excluded from the effectiveness population.
- **Neurological Assessment Evaluable (NAE) Population:** The NAE Population will include all enrolled subjects who meet the eligibility criteria, have been treated with the study catheter and had any post-ablation neurological assessment. Assessment of incidence of new lesions or deficits requires availability of the associated pre-procedural assessment.

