5.1 Primary Endpoint(s) and Associated Hypotheses

Acute Safety

The primary safety endpoint is the incidence of Primary Adverse Events (PAEs) (within seven (7) days of the initial mapping and ablation procedure). PAEs include the following AEs:

Atrio-Esophageal Fistula*	Phrenic Nerve Paralysis
---------------------------	-------------------------

Cardiac Tamponade/perforation	Pulmonary Vein Stenosis*
Death*	Stroke/CVA
Major Vascular Access Complication/Bleeding	Thromboembolism
Myocardial Infarction	TIA

**Device or procedure related death, pulmonary vein stenosis and atrio-esophageal fistula that occur greater than one week (7 days) post-procedure are considered and analyzed as primary AEs.*

Acute Effectiveness

Acute Procedural Success defined as confirmation of entrance block in all targeted PVs after adenosine and/or isoproterenol challenge. The use of a non-study catheter for PVI will be considered an effectiveness failure.

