5.2 Secondary Endpoints

- **Safety**
 - Incidence of Serious Adverse Device Effects (SADEs)
 - Incidence of Serious Adverse Events (SAEs) within 7 days (early-onset), >7-30 days (peri-procedural) and >30 days (late onset) of initial ablation procedure
 - Incidence of non-serious adverse events
 - Incidence of pre-and post-ablation asymptomatic and symptomatic cerebral emboli as determined by MRI evaluations
 - Incidence of new or worsening neurological deficits compared to baseline
 - Summary of NIHSS, mRS and MoCA scores at baseline and follow-up timepoints
- **Effectiveness**
 - PVI achieved with TGA mode only among all targeted veins and by subject
 - PVI achieved with combined use of TGA and Q-mode among all targeted veins and by subject
 - Ablation of acute reconnection (touch-up) among all targeted veins and by subject
 - Ablation by a non-study catheter among all targeted veins and by subject
 - Touch-up applications with TGA, Q-mode and non-study catheter applications
- **Additional analyses on procedural data, including but not limited to:**
 - Use of QDOT Micro™ catheter ablation outside the PV area
 - Use of a non-study catheter for ablation outside the PV area

- Total procedure time, mapping time, PV ablation time, total ablation time, RF application time, LA dwell time
- Total number of RF applications, % TGA applications and % Q-mode applications
- Anatomical location of touch-up applications
- Temperature, power, contact force, impedance
- Total Fluoroscopy time/dose

6 Levels of Significance

All data will be summarized by descriptive analyses. No formal statistical inference will be made. Sub-analyses will be done for subjects where TGA was the only application mode used and for subjects where applications were done through a combination of TGA and Q-mode. Where confidence intervals are used they will be two-sided 95% confidence intervals, unless stated otherwise.

7 Analysis Sets

The following analysis populations will be used to complete the analyses of data:

- **Safety Population (SP):** The safety population will include all enrolled subjects who have the investigational device inserted, regardless if RF energy is delivered. All safety analyses will be performed on the Safety Population.

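### A complication that ends the procedure before the study catheter is inserted falls within the wording of the primary safety endpoint but enters no safety analysis

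*Protocol*

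**What the plan says.** **Disposition.** Protocol 4.4 defines Excluded subjects as "Subjects who are enrolled but never undergo insertion of the study catheter", without limiting the reason. Of their follow-up it says "Excluded subjects will only be followed between ICF signature and exclusion for event reporting". Discontinued subjects (catheter inserted, no RF delivered) are followed for 30 days.

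**Replacement.** Protocol 4.3.2 first speaks of consented subjects who "are later found not to be eligible PRIOR to insertion of the study catheter will be excluded", and then adds "Excluded subjects can be replaced with new enrolled subjects for the study to reach a total of 50 evaluable study-subjects".

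**Analysis set.** Protocol 14.6: "The safety population will include all enrolled subjects who have the investigational device inserted, regardless if RF energy is delivered". SAP section 7 repeats the definition and adds "All safety analyses will be performed on the Safety Population".

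**Endpoint.** Protocol 3.2.1 and SAP 5.1 count PAEs "within seven (7) days of the initial mapping and ablation procedure". The list includes tamponade/perforation, major vascular access complication or bleeding, stroke and TIA.

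**Order of steps.** Protocol 8.2.2.3 puts transseptal puncture first and states "Mapping (left atrial anatomical map) is required prior to the ablation procedure". The study catheter is introduced after that. Section 8.2.2.4 allows the study catheter to be used for the mapping itself. Section 8.2.3 measures total procedure time from the first femoral puncture.

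**The concern.** The endpoint and the analysis set start at different moments. The endpoint wording takes in mapping, and the protocol's clock starts at femoral access. The Safety Population starts only when the study catheter goes in. Several listed PAEs can arise in between, during access, transseptal puncture or mapping with another catheter.

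If such an event stops the case, the subject never enters the Safety Population. The omission is then caused by the outcome being measured. The same event a few minutes later, after insertion, would count even with no RF delivered. Because the study catheter may or may not be used for mapping, the same mapping perforation could count at one centre and not at another.

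The study's stated purpose is a preliminary estimate of safety in the first use of this catheter and generator combination. With 50 subjects, one omitted event can change the headline figure from none to one.

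**Working it through.** This is mainly a check of definitions; the arithmetic gives scale. The plan states no power calculation or expected PAE rate, so there is no sample-size figure to reproduce.

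**Step 1. Follow one subject through the definitions.** Suppose a consented subject has a tamponade at transseptal puncture and the procedure is abandoned.

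| Question | Source | Result |
|---|---|---|
| Has the procedure started? | Protocol 8.2.3 (timed from first femoral puncture) | Yes |
| Is the event a listed PAE within the endpoint's wording? | Protocol 3.2.1, SAP 5.1 | Yes |
| Disposition group? | Protocol 4.4 | Excluded |
| In the Safety Population? | Protocol 14.6, SAP 7 | No |
| In the PAE or SAE tables? | SAP 7 and 10.4 | No |
| Reported as an AE/SAE? | Protocol 9.3, 9.4.1, 9.4.2 | Yes |
| Exclusion visible in the report? | Protocol 14.8.2, SAP 10.2 (all enrolled subjects) | Yes |
| Replaceable? | Protocol 4.3.2 read with 4.4 | Unclear |

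If the subject goes on to insertion despite the complication, the subject is in the Safety Population and the event counts. The gap concerns only cases that end before insertion.

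**Step 2. Follow-up rules side by side.** Section 4.4 ends event follow-up at exclusion. Section 4.3.2 has a subject withdrawn for an AE or SAE followed until it resolves or is stable. Section 9.3 has all AEs followed to resolution. These conflict for this subject. Neither of the last two sections provides a day-7 contact that would pick up a second, later event.

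**Step 3. Effect of one omitted case.** Let x be the PAE subjects among 50 evaluable subjects. Adding one omitted case changes x/50 to (x+1)/51. Intervals are exact (Clopper-Pearson) two-sided 95%.

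| As planned | From first puncture |
|---|---|
| 0/50 = 0.0% (0 to 7.1%) | 1/51 = 2.0% (0.05 to 10.4%) |
| 1/50 = 2.0% (0.05 to 10.6%) | 2/51 = 3.9% (0.5 to 13.5%) |
| 2/50 = 4.0% (0.5 to 13.7%) | 3/51 = 5.9% (1.2 to 16.2%) |

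Each case is worth about 2 percentage points.

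**Step 4. How likely is one such case?** The documents do not say. Protocol 1.4.1 gives tamponade in two earlier studies; both rates reproduce: 2/159 = 1.26% (stated as 1.3%) and 4/161 = 2.48%. Expected numbers in 50 subjects are 50 × 0.013 = 0.65 and 50 × 0.0248 = 1.24. Let f be the share of tamponades that occur before insertion. No value is given, so 10% to 50% is assumed. The chance of at least one omitted tamponade is 1 − (1 − p·f)^50:

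| p | f = 10% | f = 50% |
|---|---|---|
| 1.3% | 1 − (1 − 0.0013)^50 = 6.3% | 1 − (1 − 0.0065)^50 = 27.8% |
| 2.48% | 1 − (1 − 0.00248)^50 = 11.7% | 1 − (1 − 0.0124)^50 = 46.4% |

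The formula treats every pre-insertion tamponade as ending the case, so each figure is an upper value for tamponade at its assumed share. Bleeding, stroke and other PAEs are not included.

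**The case against.** **The set suits the objective.** Protocol section 2 asks about the safety of the catheter system with TGA, and a set defined by device insertion is a defensible choice for that. The endpoint's anchor also varies: section 2 refers to the initial ablation procedure, 9.1.3 to an ablation procedure and 14.8.4.1 to catheter ablation. This stands, and it is why the main set should not change. It does not remove the mismatch, because the endpoint definition itself (Protocol 3.2.1, SAP 5.1) and SAP 10.4 all name mapping.

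**The event is not lost.** A reader might infer that the event goes unreported or that the loss is invisible. The documents do not support that. An event during the procedure precedes the exclusion, so it falls inside even the 4.4 reporting period. AEs are reported from consent onward, SAEs within 72 hours, and disposition is tabulated and listed for all enrolled subjects. What is missing is the event's place in the safety analysis.

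**Replacement is not settled.** A reader might also infer that such subjects will be replaced. The lead-in in 4.3.2 names ineligibility only, and replacement is permitted, not required. It reaches this group only if the broader definition in 4.4 is carried over.

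**The gap may be short.** Nothing says that mapping is usually done with another catheter. Where the study catheter is used for mapping, only the access and transseptal steps remain uncovered.

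**The stakes are limited.** The study is descriptive, with no hypothesis, and the intervals with and without one case overlap heavily. This stands and lowers the severity.

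**Conclusion.** The point holds in a limited form. A subject whose procedure has started and is ended by a PAE before study-catheter insertion is missing from the PAE numerator and denominator and from every SAP safety table, although the endpoint as worded covers the event. Leaving out such a case can only lower the reported rate.

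The size per case, about 2 percentage points, rests only on the planned 50 evaluable subjects. The 6% to 46% chance of at least one case is illustrative: it depends on an assumed pre-insertion share for which the documents give no support at either end. Cases are probably few. Severity is low to moderate.

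**What to change.** 1. **Protocol 4.4:** separate subjects whose procedure started but who had no study catheter inserted from subjects excluded before the first femoral puncture.
2. **SAP 10.4:** keep the device-inserted Safety Population as the main set. Add one supplementary line giving PAEs and SAEs among all subjects from first femoral puncture, with its own denominator, and list the subjects in this group.
3. **Protocol 4.4, 4.3.2 and 9.3:** reconcile the follow-up statements so that PAE status is known for this group through the endpoint's own 7-day window.
4. **Protocol 4.3.2:** state whether replacement applies to this group. It may, provided the supplementary line is reported.

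The cost is wording in both documents, minor follow-up for a few subjects, one table line and a listing. The supplementary figure may be slightly less favourable than the main one.
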